- 2. Proforma for collection of information from study subjects(baseline survey)
- 3. Behavioural Change Communication(BCC) material
- 4. Booklet for mother
- 5. Fortnightly Pneumonia surveillance tool (Diary).

Operational Definition of Community Based Interventions (CBI): These are Behavioural Change Communication (BCC) activities conducted by ASHA/Anganwadi worker (AWW) for mothers of under five children with respect to following domains:

- 1. Child feeding practices which include exclusive breast feeding and appropriate weaning.
- 2. Immunization of under five children.
- 3. Indoor air pollution (reduction in use of biomass fuel and smoking).
- 4. Hand hygiene of mother/care taker of child: Correct hand washing steps at following 4 occasions: After defecation, after cleaning child's bottom, before food preparation, before feeding the child.
- 5. Knowledge Attitude and Practices of mother about pneumonia: Signs and symptoms of pneumonia, danger signal of severe disease and appropriate care seeking.
- 6. Cough etiquettes.

The BCC activities will include interpersonal communication, group discussions and demonstration etc. Outcome of these Community based interventions will be measured in children i.e. incidence and also deaths due to pneumonia.

Study duration: Two years.

Methodology:

The study will be conducted in phase wise manner. The activities in different phases are listed below:

Phase 1: Preparation (2 months)

- 1. Development and validation of research tools: Tools as described above will be developed and used for data collection. These tools will be quantifiable and objective. The team of investigators including paediatrician, biostatistician and anthropologist/social scientist will be involved in development and drafting of study tools. While preparing the tools available training booklets will be extensively used. All the tools will be bilingual and will be piloted for validity, question framing, relevance, sequencing and time required for filling the tools. The tools then will be finalized after making necessary modifications.
- 2. Appointment of Field supervisor (FS) and training. Training of FS
- 3. Baseline data in brief and with limited objectives will be collected from all clusters prior to randomizing them into intervention and control clusters.

Objectives of baseline survey:

- a. To obtain basic socio-demographic information of the family (age, sex, income, education & occupation)

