2. Second round of BCC activities: This will be conducted for reinforcement of the information delivered in first round. It will be conducted again in small groups after 2 months of first round and completed in two months. In this round emphasis will be given on skills acquired and demonstration by participants.

Various BCC activities will be supervised by sub-investigators.

Training of ASHA/AWW:

Investigators will train AWW & ASHA from intervention arm to orient them about the objectives, importance of project and their role in the project for surveillance.

Contents of the training modules:

- a. Introductory contents pertaining to pneumonia: protocol specific training, IMNCI guidelines for ARI/Pneumonia, diagnosis and standard management of pneumonia, problem statement of ARI/Pneumonia in their area.
- b. Surveillance related training: Fortnightly surveillance, maintenance of diary
- c. Communication skills and conducting session for mothers.
 Investigators will train all AWW and ASHA from both the arms regarding surveillance. Duration of training for ASHA/AWW:One day.

ASHA/AWW/FS from intervention arm will be requested to share their mobile numbers with mothers so that in case of any need like of sickness of child mother can contact them. The importance of response to mothers call will be emphasized as it may ensure appropriate management of child's illness and prevent the mortality. Training about fortnightly surveillance will be imparted to them.

Information about available emergency services like help line 108,102 will be given and ASHA/AWW/FS will communicate their mobile numbers to mothers/expectant mothers and will appeal to contact on same whenever the child is sick.

Phase 4: Followup and continued Intervention (12 months)

Pneumonia surveillance: This will be done in intervention arm for a period of one year by AWW/ASHA in rural area and AWW in urban slums through fortnightly house to house visit and enquiring about signs and symptoms related to pneumonia in preceding fortnight. This will help to calculate the fortnight incidence of pneumonia. Fortnightly visits will be adequate to get incidence of pneumonia in addition to this the mobile numbers of ASHA will be shared to mothers so that in case of any need like sickness of child mother can contact them. This will help to record attacks of pneumonia if any between the two fortnight visits.

Following definitions from IMNCI Guidelines will be used:

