Pneumonia: child with cough or difficulty in breathing as having pneumonia.

severe pneumonia: If the symptoms are associated with lower chest wall in drawing or subcostal retraction,

Very severe pneumonia: If there is a danger sign such as central cyanosis, or severe respiratory distress, convulsion, inability to rouse the child or if the child is unable to drink.

Interval: An episode of pneumonia after 7 days of previous episode will be counted as a new episode.

If answer is yes then ASHA/AWW will enter the information in the diary maintained by her and submit information to site investigators(SI). They will confirm the pneumonia using WHO IMNCI protocol.

Appropriate management of child's illness will be ensured. This record will be submitted in fortnightly meeting (one will coincide with their monthly meeting) with FS and the same will be updated periodically. In addition, information about any death among under five children will be collected and the cause of death will be ascertained.

Continued intervention: Will be given by field supervisor (FS) through monthly house to house visits During her house to house visits in intervention arm FS will interact with all mothers and enquire about practicing the methods, skills steps learnt during intensive intervention. In case of unsatisfactory response FS will reinforce the knowledge and skills.

The sub investigator will supervise a pair of cluster from intervention and comparison arm and will do surprise home visit to cross check information collected by AWW/ASHA.

In comparison clusters ASHA/AWW will continue their role as per existing guidelines and collect information about pneumonia and deaths due to pneumonia through fortnightly house to house visits and submitted to FS fortnightly. And AWW and ASHA will continue to

promote all activities that are part of national programme (immunisation, optimal feeding practices) in control sites.

Midterm evaluation of the project will be done by third party at the end of three months of surveillance.

Detection and referral of pneumonia cases is a part of routine activity of ASHA/AWW workers so stopping of these duties is not advisable. And they will be closely monitored by field supervisors and sub investigators.

Standard care for ARI / Pneumonia will be provided to referred children through our own institutions and partner in public sector in two districts.

Phase 5: Data Analysis (2 months) and Final Report writing (1 month)

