1. Information about Incidence of pneumonia will be generated and findings will be compared to determine the change in intervention and control clusters. Separate analysis for overall change in childhood mortality and morbidity will be done.

Report will be shared with all stakeholders for review, discussion and comments. Final report will be prepared by incorporating comments. The final report will be shared in the closure meeting and then submitted to the funding agency.

Continuous monitoring: Will be done through on job supervision and monthly review meetings with all the stakeholders.

Process indicators:

- 1. Evaluation of competencies learned by ASHA through training
- 2. Percentage of mothers trained in first round of BCC activities.
- 3. Percentage of mothers trained in second round of BCC activities.
- 4. Percentage of children diagnosed with pneumonia (fortnightly)
- 5. Number of cases cross checked by the field supervisor per month
- 6. Number of cases cross checked by the sub-investigator per month.

Key Outcomes:

Primary Outcome-Incidence of pneumonia in both the arms will be calculated and compared. Secondary Outcome-Morbidity rates including diarrhea in both the arms.

Data Management: Procedures involving design of data collection forms, data entry system and data quality management will be outsourced to a reputed statistical firm which has senior statistician with PhD with more than 15 years of experience of handling various international projects.

Data collection and entry: Each study subject will have a unique serial number which will be mentioned on every tool. Validity checks for the data will be applied and outliers will be confirmed.

Plan of data analysis: Data will be analyzed and summarised as proportions, percentages, mean and standard deviation. Data will be analyzed using STRATA (version 6.0).

Data Preservation:

All hard copies of the study tools and other study documents will be archived for at least five years after submission of final report in the department of Community Medicine, BVU Medical College, Pune. Soft copies will be stored in DVDs and external hard disc for minimum seven years. The data if requested may be shared for the purpose of research in future at other sites with due acknowledgement.

Timeline of the research:

Activity											N	lor	nth	S										
	_	7	3	4	2	9	7	8	6	10	11	12	13	14	15	16	17	18	19	50	21	22	23	24
Phase 1: Preparation										•	`	`	•	•	`	`	•	`	•					

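### The follow-up text gives no single death-collection rule for both arms, although pneumonia deaths and overall mortality are to be reported

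*Protocol*

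**What the plan says.** Two places in the protocol commit the trial to mortality results. The Operational Definition of Community Based Interventions states: "Outcome of these Community based interventions will be measured in children i.e. incidence and also deaths due to pneumonia". Phase 5 (Data Analysis) adds: "Separate analysis for overall change in childhood mortality and morbidity will be done". Key Outcomes does not list mortality; after pneumonia incidence it has only: "Secondary Outcome-Morbidity rates including diarrhea in both the arms".

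Collection of deaths during follow-up is described in Phase 4. The Pneumonia surveillance text opens with "This will be done in intervention arm for a period of one year". It goes on to the case definitions, the rule for counting a new episode and the confirmation of cases, and then says that "information about any death among under five children will be collected and the cause of death will be ascertained". A later paragraph of the same phase sets out what happens in comparison clusters. There the workers continue their existing role and "collect information about pneumonia and deaths due to pneumonia through fortnightly house to house visits", reporting to the field supervisor each fortnight.

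**The concern.** A mortality comparison needs the same deaths to be sought, and their causes assigned in the same way, in both arms. The Phase 4 text, followed to the letter, asks for every under-five death with its cause in one arm and for pneumonia deaths alone in the other.

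Two results are at stake. The overall mortality analysis in Phase 5 would have no matching count from the comparison clusters. The pneumonia-death outcome would exist in both arms, but a cause-ascertainment step is stated only in the text introduced as intervention-arm surveillance. A statistical analysis plan cannot repair this later, because deaths that the field workers never recorded cannot be recovered at analysis.

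**Working it through.** **Passages side by side**

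- Baseline survey (Phase 1): child mortality over the previous year, including pneumonia mortality, in all clusters before randomisation. Both quantities are measured in both future arms.
- Follow-up, surveillance text (Phase 4): any under-five death, with cause ascertained. The sentence names no arm; the text that contains it is introduced as intervention-arm work.
- Follow-up, comparison paragraph (Phase 4): pneumonia episodes and pneumonia deaths. Other deaths and cause ascertainment are not mentioned.
- Opening summary: fortnightly surveillance in both arms, but of pneumonia; deaths are not mentioned.
- Training of ASHA/AWW (Phase 3): workers of both arms are trained in surveillance; deaths are not mentioned.

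No place provides for all-cause death collection in comparison clusters during follow-up.

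**How many deaths are involved**

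The protocol gives no mortality rate, mortality effect or mortality power, so there is no stated figure to reproduce. The inputs are:

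- About 4,800 children in two equal arms of 8 clusters (section 5, sample size): 4,800 / 2 = 2,400 per arm. One year of surveillance gives about 2,400 child-years per arm.
- Pneumonia share of under-five deaths: 14% (section 2, Problem statement). This is a background figure, not an estimate for these clusters.
- Under-five death rate: not given. Assumed 5 to 10 per 1,000 child-years, with 2 per 1,000 as a low case.

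Deaths per arm = 2,400 x rate; pneumonia deaths per arm = that number x 0.14.

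- At 2 per 1,000: 4.8 deaths, 0.7 from pneumonia.
- At 5 per 1,000: 12 deaths, 1.7 from pneumonia.
- At 10 per 1,000: 24 deaths, 3.4 from pneumonia.

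With 1.7 to 3.4 expected pneumonia deaths, assigning the cause of a single death differently changes an arm's count by 1/3.4 to 1/1.7, about 30% to 60%. The direction cannot be known in advance.

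**Literal-reading bound for all-cause mortality**

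Suppose one arm counted all deaths and the other only the share s due to pneumonia, and the two counts were then divided as if both were all-cause. With no true effect, the apparent ratio (intervention over comparison) would be 1/s. At s = 0.14 this is 1/0.14 = 7.1; for assumed shares of 10% to 30% it is 10.0 to 3.3. With the same rule in both arms the expected ratio is 1.00. This bound describes a misuse of the data that the protocol does not plan. It is not a forecast.

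**The case against.** The strongest reply is that the arm difference is inferred. The sentence on any death names no arm, and the summary and the training section both point to surveillance shared by the two arms. If everything under the Phase 4 surveillance heading applied to the intervention arm alone, so would the pneumonia definitions, the new-episode rule and the confirmation of cases, although pneumonia incidence is the primary comparison. That makes loose drafting a likely explanation. This stands, and it limits the point to what the text allows to happen. It does not remove it: the comparison paragraph is explicit and narrower, and a field worker who follows it has no instruction to record other deaths.

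A reader might infer two stronger things. One is that comparison-arm causes would rest on worker opinion against properly ascertained causes in the other arm. The protocol does not say who assigns cause in either arm, and it has a sub-investigator supervise a pair of clusters, one from each arm, and cross-check the workers' information by surprise visits. The other is that a roughly seven-fold false mortality ratio should be expected. That needs an all-cause count divided by a pneumonia-only count, which no section plans.

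It is also fair to say that Phase 5 does not state that its mortality analysis is between arms, and that mortality is in neither the sole objective nor Key Outcomes. Even a before-and-after account of overall mortality in the comparison clusters, however, would lack its follow-up figure.

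**Conclusion.** The point holds in a limited form. The protocol promises pneumonia-death and overall-mortality results but does not state one follow-up rule for collecting deaths in both arms. Read literally, all-cause mortality could not be compared between arms. Pneumonia mortality could be compared, but with possible differential cause assignment of unknown size and direction. The documents do not establish that deaths will in fact be collected differently or that a biased result will follow.

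The primary outcome is not the subject of this point. With about 12 to 24 deaths per arm at the assumed 5 to 10 per 1,000 child-years, and about 2 to 3 of them from pneumonia if the 14% share applies, mortality can only be described. The point should be settled before surveillance starts, because it concerns what is recorded in the field.

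**What to change.** Replace the two Phase 4 statements on deaths with one that names both arms: every under-five death is recorded at the fortnightly visit, and its cause is ascertained by the same procedure whatever the arm. Tying the rule to the fortnightly visit matters because intervention clusters also have monthly home visits by the field supervisor, which give an additional chance to hear of a death.

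Under Key Outcomes, add all-cause deaths and pneumonia deaths as descriptive secondary outcomes, reported by arm with no efficacy claim, so that the list agrees with the Operational Definition and Phase 5.

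The cost is protocol wording and use of the same cause-of-death form in the comparison clusters, for about 12 to 24 deaths at the assumed rate.

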Aim: To assess the efficacy of community based interventions in reducing incidence of pneumonia.

Objectives:

To compare the incidence of pneumonia among under five year children from intervention and comparison clusters after selected community based interventions.

[figure not shown]
5. Study Protocol/Detailed research plan:

Study design: A cluster randomized trial in Pune and Sangli district stratified by urban slums and villages.

Study area: Bharati Vidyapeeth University is a multidisciplinary and multi centric university having two medical colleges in Pune and Sangli districts of Maharashtra state of India. This study will be carried out in 4 sites under the urban and rural field practice area of these two medical colleges. Each site is having 9-16 clusters of slums/ villages.

Number of clusters and sample size calculation:

Figure-1

A review article indicates that incidence of childhood pneumonia is 0.2 to 0.5 per child per year (Ghimire M. et al 2012). This is equivalent to 20% to 50% of incidence of pneumonia. For sample size calculations we have assumed the incidence rate at 30%. Community based intervention is expected to reduce the incidence rate by 50%. The curve required for various powers and number of clusters is shown in figure-1. Sample size assumptions and estimations are reviewed by a statistician.

To achieve 80% power and assuming intra-class coefficient of variation to be 0.5, the study will need to enrol minimum 15 clusters of average 300 size. However we have decided to include 16 clusters.

Thus the total number of children under 5 years to be enrolled in the study will be about 4800.

The field practice areas of both medical colleges together have 47 available clusters; 16 clusters will be selected randomly and allocated to intervention arm and comparison arm by randomization. Thus there will be 8 clusters in intervention arm and equal number in comparison arm.

All under five year children residing in the selected clusters and their mothers (including expectant mothers) will constitute study subjects. The process of inclusion of subjects (mothers and children) will continue throughout the study period. Those children who complete five years of age in the project period will be excluded. However, these children will be considered while calculating denominator of children-months.

Study tools: Following tools will be developed and used for data collection and intervention

- 1. Trainer's modules

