- b. To determine proportion of women in reproductive age group

- c. To determine incidence of pneumonia in last one year and incidence of ARI in last one month and also to measure child mortality in last one year including mortality due to pneumonia.
- d. To determine sources contributing to indoor air pollution like type of fuel used for cooking, smoking by family member, overcrowding.
- e. To measure proportion of other risk factors like low birth weight, birth order, malnutrition, breast feeding, immunization status of under five year old and KAP of mother about pneumonia including care seeking behavior.
- 4. Intervention cluster will be geographically separated so as to reduce contamination. There are minimal chances of contamination however some may occur during nonformal communication of ASHA AWW with each other.
- 5. Identification and orientation of private medical practitioners, concerned Taluka Health Officer, Medical Officers, Auxiliary Nurse Midwives (ANM).
- 6. Accredited Social Health Activist (ASHA), Anganwadi workers (AWW) from the selected clusters will be identified and they will be incentivized through the project.

Field supervisors will be trained regarding

- a. Introductory contents pertaining to pneumonia: protocol specific training, IMNCI guidelines for ARI/Pneumonia, diagnosis and standard management of pneumonia, problem statement of ARI/Pneumonia in their area.
- b. Intervention related training: Relevance of selected risk factors in reduction of pneumonia. Methods to reduce the same through Behavioural Change Communication activities.
- c. Surveillance related supervisory training:
- d. Communication skills and conducting session for mothers above mentioned areas. Over and above their role as a supervisor will be explained and taught to them.
- e. Initial Training: Two days and one additional day for hands on training in the field. The material intended to be used by them for Behavioural change communication (BCC) during interpersonal communication with mothers will be shared with them and their competency will be assessed in the field through demonstration of conducting a BCC session for mothers.

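### The outcome is defined as an episode rate over child-months, but the stated analysis lists only proportions, percentages, means and SDs and does not carry the cluster design through

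*Protocol*

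**What the plan says.** **Outcome.** Key Outcomes (Protocol, section 5) gives "Primary Outcome-Incidence of pneumonia in both the arms will be calculated and compared" and does not say whether incidence is a rate or a risk. Other parts of section 5 point to a rate. Phase 4 states that "An episode of pneumonia after 7 days of previous episode will be counted as a new episode". The paragraph on study subjects lets mothers and children enter throughout the study and uses a child-months denominator.

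**Children who turn five.** The same paragraph says "Those children who complete five years of age in the project period will be excluded" and then that "these children will be considered while calculating denominator of children-months".

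**Analysis.** Plan of data analysis says "Data will be analyzed and summarised as proportions, percentages, mean and standard deviation" and names a software package. Phase 5 adds that "findings will be compared to determine the change in intervention and control clusters". No unit of analysis, test, interval or model is named.

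**Design and sizing.** The design is "A cluster randomized trial in Pune and Sangli district stratified by urban slums and villages", with 8 clusters per arm of about 300 children each. The sample size section equates 0.2 to 0.5 episodes per child per year with 20% to 50%, plans on 30% halved by the intervention, and uses a between-cluster variation term of 0.5. The baseline survey, done before randomisation, aims "To determine incidence of pneumonia in last one year and incidence of ARI in last one month".

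**The concern.** Three things do not fit together.

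- **The measure.** None of the listed summaries is a rate per unit of child-time. A child with three episodes counts three times in a rate and once in a proportion. A child who enters late or leaves early adds partial time to a rate and has no natural place in a simple percentage. Two analysts following this text could report different primary results.
- **The design.** The sizing allows for variation between clusters, but the analysis sentence mentions neither clusters nor strata. If it were carried out on individual children, the precision claimed would be that of about 4,800 independent units when only 16 were randomised.
- **The age-out rule.** A child who is excluded from the study but kept in the denominator may contribute time without episodes.

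At stake are a primary result with one meaning, and a significance test that can be believed if a reduction is reported.

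**Working it through.** **1. The protocol's own equivalence.** Multiplying 0.2 and 0.5 per child-year by 100 gives the protocol's 20% and 50%. That holds only if no child has more than one episode. With Poisson episodes over a full year (an assumption), the proportion with at least one episode is 1 − exp(−rate):

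| Rate per child-year | Proportion affected |
|---|---|
| 0.20 | 18.1% |
| 0.50 | 39.3% |
| 0.30 (planned control) | 25.9% |
| 0.15 (planned intervention) | 13.9% |

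The range becomes 18% to 39%. A halved rate becomes a risk ratio of 13.9/25.9 = 0.54, not 0.50.

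**2. What a child-level test would do (conditional).** Inputs from the protocol: rate λ = 0.30 per child-year, 300 children followed for one year (y = 300 child-years per cluster), 8 clusters per arm. The value 0.5 is read as a between-cluster coefficient of variation k; the protocol's term for it mixes that with an intra-class correlation. A two-sided 5% level is assumed, as none is stated.

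With no true effect:
- Within-cluster variance: λ/y = 0.30/300 = 0.001
- Between-cluster variance: k²λ² = 0.25 × 0.09 = 0.0225
- Design effect: 1 + 0.0225/0.001 = 23.5
- Type I error of a pooled test: 2 × [1 − Φ(1.96/√23.5)] = 0.69

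| k | Design effect | Type I error |
|---|---|---|
| 0.5 (protocol value) | 23.5 | 69% |
| 0.25 (assumed) | 6.6 | 45% |
| 0.1 (assumed) | 1.9 | about 15% |

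Simulation of 20,000 trials with gamma-distributed cluster rates gave 68%, 45% and 15% for the pooled test. A t-test on the 16 cluster log-rates rejected in about 5% at each k. If 0.5 were instead an intra-class correlation, the design effect would be 1 + 299 × 0.5 = 150.5 and the type I error about 87%.

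At the planned effect, the within-cluster variance terms sum to (0.30 + 0.15)/300 = 0.0015, and the between-cluster terms to 0.25 × (0.09 + 0.0225) = 0.0281. The ratio of cluster-based to naive standard error is √(0.0296/0.0015) = 4.4. The 95% half-width for the rate difference of 0.15 is 0.027 naively and 0.131 at cluster level (14 df).

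**3. Age-out rule.** Assume even ages, incidence that does not vary with age, and a stable cohort. One fifth of children turn five in the surveillance year and give half a year each on average: 1/5 × 1/2 = 10% of child-time. If their time counts and their episodes do not, 0.30 and 0.15 become 0.27 and 0.135. The rate ratio stays at 0.50.

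**4. Baseline adjustment.** On the rate-difference scale, power at 8 clusters per arm is 63% unadjusted (standard error √(0.0296/8) = 0.061, 14 df). If baseline and follow-up cluster rates correlate at r, the between-cluster variance is multiplied by 1 − r². On 12 df this gives 66% at r = 0.3, 74% at r = 0.5 and 87% at r = 0.7. All three correlations are assumed.

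**The case against.** A reader might infer that the trial will test about 4,800 children as independent, so that its tests and intervals will be far too narrow. The document does not support that. The analysis sentence names no unit and no test, and Phase 5 speaks of comparing clusters. Means and SDs can summarise cluster rates, which is just what a cluster-level t-test needs. The sizing shows that the authors knew of clustering, and a statistical analysis plan that is not shown may specify a clustered analysis. This objection stands: the type I figures are conditional, and the lack of a named model is not in itself an error.

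It is also fair to say that the ordinary open-cohort reading of the age-out rule is harmless: a child leaves at the fifth birthday and the months already contributed are kept. A reader might infer a biased treatment comparison, but the rule applies to both arms and leaves the rate ratio almost unchanged. What remains is an ambiguity that affects absolute rates.

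Nor is it an error to leave baseline incidence out of the analysis. An unadjusted cluster comparison is valid. The baseline is a one-year recall survey, while follow-up is fortnightly surveillance with confirmation, so their correlation is unknown.

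The conflict between a recurrent-episode rate and a list of proportions and percentages is untouched by these points. It lies in the protocol's own text.

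**Conclusion.** The concern holds in a limited form. The protocol defines a recurrent-episode rate over child-months, yet sizes and summarises the outcome as percentages. At the planning values the two differ by about 4 percentage points in the control arm (30% against 26%) and about 1 in the intervention arm (15% against 14%), under a Poisson assumption. The analysis sentence does not carry through the clusters, the strata or the variation term.

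The consequence for inference depends on how the analysis is done. A child-level test would have a type I error of about 69% at k = 0.5, and about 15% even at an assumed k of 0.1. A cluster-level test keeps about 5%. The age-out wording could lower absolute rates by up to about 10% on its literal reading, with little effect on the rate ratio.

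**What to change.** Amend Key Outcomes, the paragraph on study subjects and Plan of data analysis as follows:

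1. Name the primary measure as confirmed pneumonia episodes per child-month, and stop equating episodes per child-year with a percentage of children.
2. For children who reach five, count both episodes and child-months up to the fifth birthday, and neither afterwards.
3. State that the primary comparison uses the log episode rate of each of the 16 clusters, regressed on arm and slum/village stratum. Adding the cluster's baseline pneumonia incidence is an inexpensive improvement. Report a rate ratio with a 95% confidence interval from the t distribution, with 16 − 4 = 12 df (13 without baseline).
4. Keep proportions, means and SDs for description.

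The cost is wording only, since the data are already due to be collected. Intervals will be wider than those from an analysis that ignores clusters, which is the honest width. Baseline adjustment costs one degree of freedom, and its gain in power is illustrative and should not be relied on for sizing.
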